5.3.2 ELIGIBILITY CRITERIA

Eligibility will be determined by a phone screen provided by a research assistant, supervised by the PI.

Inclusion/Exclusion Criteria Phase 1 (A & B):

Participants will be included if they 1) have an International Classification of Headache Disorders – 3 beta diagnosis of migraine, 2) self-report between 6 to 14 headache days per month, 3) are currently prescribed a triptan for acute migraine management, 4) are between the ages of 18 and 65, and 5) self-report at least one problem with adherence to preventive and acute migraine management strategies.

Exclusion criteria are 1) probable or confirmed medication overuse headache, 2) a plan to change, or changing preventive or acute migraine medication during study participation, and 3) are pregnant or are planning to become pregnant during study involvement (as triptans are Category C medications).

Inclusion/Exclusion Criteria Phase 2:

Participants will be included if they 1) have an International Classification of Headache Disorders – 3 beta diagnosis of migraine, 2) self-report and diary-confirmed 6 to 14 headache days per month, 3) are currently using one of the following treatments for acute migraine management: triptans, ditans, gepants, NSAIDs, or acetaminophen, 4) are stable on current preventive and acute treatment regimen for migraine, 5) are between the ages of 18 and 65, 6) reads English, 7) has capacity to consent, and 8) complete 80% of diary recordings in the first 30 days of monitoring.

Exclusion criteria are 1) probable or confirmed medication overuse headache, 2) a plan to change, or changing preventive or acute migraine medication during study participation, 3) are pregnant or are planning to become pregnant during study involvement (as triptans are Category C medications), 4) psychiatric illness or cognitive difficulties that would interfere with participation in the study, and 4) participated in Phase 1 of the Clinical Decision Support for Patient Migraine Management protocol.

Inclusion/Exclusion Criteria Phase 3:

Participants will be included if they 1) completed Phase 2 of the study, 2) completed at least 80% of diary recordings throughout Phase 2 of the study, and 3) demonstrated poor (<50%) adherence to at least one acute migraine management strategy and at least one preventive behavioral migraine management strategy during study Phase 2.

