6.2 Assessments

6.2.1 Efficacy

The primary outcome variables will be **adherence to acute and preventive migraine management strategies**. All primary outcome variables will be assessed through the daily electronic headache diary, collected through the Status/Post app and captured by the REDCap system.

Adherence to Acute Migraine Management Strategies.

	When assessed	Question asked	Indication of adherence	Indication of non-adherence
Stress	each evening	whether they used a stress management strategy today	Yes	No
Sleep	each morning	when they got in and rose out of bed	Within one hour of median	Outside of one hour of median
Eating	each evening	whether they ate at least three times that day	Yes	No

Treat Early: When participants record headache activity, they will record type, timing, and current pain level for each acute medication dose taken. Treating early is operationalized as taking acute medication while the pain is mild.

Avoid Overuse: Avoiding overuse is operationalized as taking fewer than 10 triptans and 15 NSAIDS/acetaminophen per month.

Adherence to Preventive Migraine Management Strategies:

Adherence to Preventive Behavioral Strategies: Each participant will record information related to a single strategy: stress management, sleep management, or consistent eating. Participants will record either 1) whether they used a stress management strategy today (assessed each evening; Yes = adherent, No = non-adherent), or 2) when they got in and rose out of bed (consistent bedtime and rise-time; assessed each morning; Within 1 hour of median = Adherent, outside of 1 hr of median = Non-Adherent), or 3) whether they ate at least three times that day (consistent eating, assessed each evening; Yes = Adherent, No = Non-adherent).

Adherence to Preventive Medication: If a participant is taking a preventive medication, they will record whether they took preventive medication each day. Taking preventive medication = Adherent, Not taking preventive medication = Not-adherent.

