6.4 Statistical Method

6.4.1 Statistical Design

Basic descriptive statistics (e.g., means, standard deviations, frequencies) for variables of interest will be computed. Graphical approaches will be used to further explore the data where appropriate. The outcomes are either 1) repeated measures of binary adherence to each migraine management strategy [coded each day as 0 (did not adhere) or 1 (adhered)] or total number of non-adherence days for each migraine management strategy over the relevant time-frame. Longitudinal binary outcomes will be analyzed using randomized logistic models, and number of total non-adherence days will be examined using Poisson regression models. SAS 9.3 will be used in the analyses. All tests are two-sided using significance level 0.05.

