6.4.2 Sample Size Considerations

Based on n=30 subjects in CDST and Headache Education Control groups, and assumptions of dropout rate and correlations as described in the initial phase of the study, we will have 80% power to detect an odds ratio of 1.28 in adherence to migraine management strategies between CDST and Headache Education Control.

For Phase 1b, we would like to estimate satisfaction, usability, and attrition over the course of the month of diary use. In our previous daily diary research, approximately 60% of participants do not continue using headache diary applications after 3 days, and approximately 30% of people adhere to the daily diary for the duration of a 30-day study. Therefore, we hope to obtain information from n=60 people regarding satisfaction and usability at the end of the 30-day period.

For the main phase of the study, based on estimated proportions of 0.37 for stress management, 20% with mood disorder and 30% male, cumulative drop-out rate of 0.073, 0.172 and 0.216 at the end of 1, 2, and 3 month, respectively, from previous studies 1, and assuming correlations of no more than 0.6 among repeated daily migraine management strategies, with n=100 participants, we can detect odds ratios of 1.29 between those with and without mood disorder, 1.26 between female and male, and 1.17 corresponding to 1 SD difference in continuous predictors, with 80% power.

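### Section 6.4.2 states its detectable odds ratios without limiting them to one outcome, but Avoid Overuse cannot reach the stated 80% power, and Treat Early, scored once per treated headache day, reaches it only near 14 headache days a month

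*Combined protocol and SAP*

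**What the plan says.** Section 6.4.2 gives the Phase 3 figure: "we will have 80% power to detect an odds ratio of 1.28 in adherence to migraine management strategies between CDST and Headache Education Control". For this figure it carries over drop-out and correlations from the earlier phase, but does not mention a baseline proportion. The main-phase paragraph of the same section is "based on estimated proportions of 0.37 for stress management", with "assuming correlations of no more than 0.6 among repeated daily migraine management strategies". For 100 participants it lists detectable ORs of 1.29 (mood disorder), 1.26 (gender) and 1.17 (per SD of a continuous predictor), without tying them to one outcome. Section 6.4.1 adds "All tests are two-sided using significance level 0.05".

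The primary outcomes in 5.2.1 and 6.2.1 (Efficacy) differ in how often they yield a value:

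- Behavioural strategy: one value per day. Each participant records one of stress, sleep or eating.
- Avoid Overuse: "Avoiding overuse is operationalized as taking fewer than 10 triptans and 15 NSAIDS/acetaminophen per month".
- Treat Early: "Treating early is operationalized as taking acute medication while the pain is mild". Pain level is recorded for each acute dose.
- Preventive medication: "If a participant is taking a preventive medication, they will record whether they took preventive medication each day".

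Section 5.3.2 admits people with "self-report and diary-confirmed 6 to 14 headache days per month". Section 6.4.1 nevertheless describes adherence to every strategy as scored daily, 0 or 1, or as a total of non-adherent days. No proportion, observation count or power is given for either acute outcome or for preventive medication.

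**The concern.** A detectable OR depends on how many informative observations each person contributes. A daily behaviour gives about 90 over three months, a monthly status gives 3, and an outcome that exists only when a dose is taken gives something in between. A figure built on daily stress-management data cannot simply be extended to the others.

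The stakes lie in interpretation. The hypotheses in 4.1 cover acute as well as preventive adherence, Phase 3 enrols people with poor adherence to at least one acute strategy, and every CDST participant receives the Medication module (6.1). A null acute result would be read against a stated 80% power that the acute outcomes do not have, and could be taken as evidence that the tool does not work.

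**Working it through.** **Inputs.** Two-sided alpha 0.05 (6.4.1). Phase 3: 30 per arm, OR 1.28 (6.4.2). Phase 2: n = 100, 30% male, 20% with mood disorder (6.4.2). Proportion 0.37; its use for Phase 3 is an inference. Three months are taken as 90 days. Cumulative drop-out is 0.073, 0.172 and 0.216, so mean retention, interpolated within months, is (0.9635 + 0.8775 + 0.806)/3 = 0.882.

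**Formula.** For a log odds ratio, information I = n × v × p(1−p) × m. Here v is the predictor variance (0.25 for 1:1 allocation, 0.3 × 0.7 = 0.21 for gender, 0.2 × 0.8 = 0.16 for mood disorder, 1 per SD) and m is the number of independent observations per person. Power = Φ(|ln OR|√I − 1.96) plus a negligible opposite tail. The 80% detectable OR is exp(2.80/√I). Positive within-person correlation only lowers I for a between-group contrast, so zero correlation is the most favourable case. For OR 1.28, 80% power needs I = (2.80/0.247)² ≈ 129.

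**The plan's own figure, daily outcome, all 60 contributing.** I = 60 × 0.25 × 0.2331 × 90 × 0.882 = 278.

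- Zero correlation: power 98%, detectable OR 1.18.
- AR(1) at 0.6 (design effect about 3.9): I = 71, power about 55%, OR 1.39.
- Exchangeable at 0.6 (design effect 1 + 78.4 × 0.6 = 48): I = 5.8, power about 9%, OR about 3.2.

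The stated 1.28 needs a design effect of 278/129 ≈ 2.2, roughly AR(1) 0.37 or exchangeable 0.015. It is reachable for a daily outcome, but not at a correlation of 0.6 under either structure.

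**Avoid Overuse, m = 3, zero correlation, no drop-out.** At p = 0.5, the most favourable value, I = 60 × 0.25 × 0.25 × 3 = 11.25. Power is 13% and the detectable OR is exp(2.80/3.354) = 2.3. At p = 0.9 (assumption), I = 4.05, power 8%, OR 4.0. Phase 2 at p = 0.5:

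- Gender, OR 1.26: I = 15.75, power 15%.
- Mood disorder, OR 1.29: I = 12, power 14%.
- Per SD, OR 1.17: I = 75, power 27.5%.

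**Treat Early, one value per treated headache day, a dose on every headache day, p = 0.37, zero correlation.** Six to 14 days a month give 18 to 42 values per person.

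| Headache days/month | m | Power, no drop-out | Power, plan's drop-out |
|---|---|---|---|
| 6 | 18 | 50% | 45% |
| 8 | 24 | 62% | 57% |
| 10 | 30 | 72% | 66% |
| 12 | 36 | 79% | 74% |
| 14 | 42 | 85% | 80% |

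At 10 days with drop-out, I = 92.6 and the detectable OR is exp(2.80/9.62) = 1.34. In Phase 2, on the same basis with drop-out, power at 6 to 8 days is 53–65% for gender and 50–62% for mood disorder. For OR 1.17 per SD it is 86% or more across the range, so that figure is not short for Treat Early.

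**Cross-check.** A two-proportion calculation needs 1,076 independent observations per arm at p = 0.37, and at least about 1,032 at any baseline rate. Avoid Overuse supplies 30 × 3 = 90. Treat Early supplies 540 to 1,260 before drop-out and 476 to 1,112 after it, with power 46–81% after drop-out.

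**Preventive medication.** Only users contribute, so information shrinks with the share of users. The documents do not give that share, so no figure can be computed.

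**The case against.** Four objections carry weight.

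- **Daily coding.** Section 6.4.1 scores every strategy each day, which might seem to give Avoid Overuse 90 values. It conflicts with the monthly definition in 5.2.1 and 6.2.1, and repeating a monthly status on 30 days adds no information. What stands is that the unit of analysis has to be reconciled.
- **Doses, not days.** Pain level is recorded for each dose, so 18 to 42 is not a true ceiling for Treat Early. With 1.5 scored doses per headache day (assumption) treated as independent, the drop-out figures become about 62%, 74%, 83%, 89% and 93% at 6, 8, 10, 12 and 14 days. Doses within a day would be correlated and untreated days lower the count, but a reader should not infer that Treat Early falls short over most of the eligible range whatever the scoring rule.
- **Source of 0.37.** The Phase 3 sentence does not carry it over. This stands as a caveat, but Avoid Overuse fails at any proportion.
- **It is a pilot.** Phase 3 serves the secondary objective and is meant to yield initial effect sizes (3.3.1, Potential Benefits). Nothing in the plan says non-significance will be read as no effect. That argues for correcting the statement, not for enlarging the trial.

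A reader might also infer that the four ORs are sound for the daily behavioural outcome. The documents do not support that: 1.28 does not reproduce at 0.6, and each participant is said to record a single behavioural strategy. If 20 of 60 recorded stress (assumption), power at zero correlation with drop-out would be 66%. The diary contents in 6.1.3 list sleep, eating and stress items without restricting them to a subset, so the number contributing is unclear.

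**Conclusion.** The point holds for Avoid Overuse without reservation about correlation, drop-out or baseline rate: Phase 3 power is at most about 13% against a stated 80%, and all three Phase 2 ORs fail as well. It rests only on the monthly definition.

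For Treat Early it holds conditionally. With one value per treated headache day, p = 0.37, zero correlation and the plan's drop-out, OR 1.28 has 80% power only at about 14 headache days a month. For preventive medication, power is below that of the full sample by an unknown amount.

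It would be tempting to call 1.28 a proven miscalculation. The plan says only that correlations do not exceed 0.6 and gives no structure, so this is a gap in reporting. The calculations concern the between-group contrast and do not assess the Group × Time term in 6.4.3.2.

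**What to change.** In 6.4.2, stop stating the ORs for all strategies together. For each OR, name the outcome, baseline proportion, observations per person, number of participants contributing and correlation structure. Recompute 1.28, 1.29, 1.26 and 1.17 on that basis, including for the daily behavioural outcome.

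Reconcile 6.4.1 with 5.2.1 and 6.2.1 on the unit of analysis for Avoid Overuse and Treat Early. For Treat Early, say whether a day or a dose is scored and how untreated headache days are handled. Then give a separate detectable OR for each: in Phase 3, no better than about 2.3 for Avoid Overuse, and about 1.34 for Treat Early at 10 headache days a month if one value per day is scored. For preventive medication, compute on the expected number of users.

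State that the Phase 3 acute outcomes will be reported as estimates with 95% confidence intervals, and that non-significance will not be read as absence of effect.

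The cost is a rewritten power paragraph and a short clarification of the outcome definitions, with no additional participants or data. The downside is that the stated detectable effects become less favourable.

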6.3 Study Procedures

6.3.1 Study Schedule

Phase 1A

Screening and Enrollment: Up to 50 potential participants will be screened to identify 24 participants eligible and interested in the study. Potential participants will be contacted by phone or email by the research coordinator to be screened for inclusion criteria. If participants meet inclusion criteria and are interested in study participation, the research coordinator will provide informed consent over the phone (see "CDST stamped Oral Consent Form", previously approved).

Study Procedures: Participants will then receive an email from the research coordinator (see "CDST - App download email" attached) with instructions to download the study app. Participants will download the study app onto their device and will receive either the CDST or Headache Education version of the app. Participants will use the app, including three daily diary entries, for one week. After one week, the PI will have conduct a focus group interview with each participant (see "Focus Group Seed Questions 11.10.15" previously approved). Once the focus group is completed, the research coordinator will send the participant a thank you email (see "CDST - Thank you emails "attached) with an attached gift card compensation (\$30).

[figure not shown]
Phase 1B

Screening and Enrollment: Up to 500 potential participants will be screened to identify 250 participants eligible and interested in the study. Potential participants may be contacted by phone or email by the research coordinator to be screened for inclusion criteria. If participants meet inclusion criteria and are interested in study participation, they will provide informed consent via the REDCap app.

Study Procedures: Participants will then receive an email from the research coordinator (see “CDST - App download email” attached) with instructions to download the study app. Participants will download the study app onto their device. Participants will use the app, making one daily diary entry, for one month. After one month, the PI may conduct a focus group interview with each participant (see “Focus Group Seed Questions 11.10.15” previously approved). Once participation completed, the participant will be entered in a raffle for one of three \$200 gift cards as compensation.

Phase 2 and 3

Figure 6.3.1. Phase 2 and 3 Study Schedule

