6.3.6 End of Study and Follow-Up

At Month 7, participants will complete a long battery of surveys they have been completing throughout the study; additional surveys are the CSQ and Program Evaluation Surveys. If a participant is randomized to an intervention group but discontinues participation in the study for any reason prior to Month 7, they will be asked to complete the CSQ and Program Evaluation Surveys. Adverse Events are assessed by research coordinator contacts bi-weekly throughout the study. If a participant withdraws from the study early for any reason, we will complete this assessment at that time.

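### Phase 1B plans satisfaction and usability data from about 60 of 250 enrollees at day 30 and describes no assessment of early stoppers, so the estimate will mainly describe persisters

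*Combined protocol and SAP*

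**What the plan says.** Section 6.4.2 gives the aim: "For Phase 1b, we would like to estimate satisfaction, usability, and attrition over the course of the month of diary use". From the team's previous diary research it expects that "approximately 60% of participants do not continue using headache diary applications after 3 days" and that "approximately 30% of people adhere to the daily diary for the duration of a 30-day study". It presents the target as following from those rates: "we hope to obtain information from n=60 people regarding satisfaction and usability at the end of the 30-day period".

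Section 6.3.1 sets enrolment: "Up to 500 potential participants will be screened to identify 250 participants eligible and interested in the study". The only occasion it describes for collecting opinions in Phase 1B is optional and comes at the end: "After one month, the PI may conduct a focus group interview with each participant". On the incentive it says: "Once participation completed, the participant will be entered in a raffle for one of three \$200 gift cards as compensation". Section 6.3.5 lists user interface and overall satisfaction among the focus-group topics. The two satisfaction questionnaires, the CSQ and the Program Evaluation, appear in the timing table only at Month 7, under Phases 2 and 3.

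For people randomised in Phase 3 who discontinue before Month 7, section 6.3.6 says "they will be asked to complete the CSQ and Program Evaluation Surveys". That section's closing provision for early withdrawal concerns adverse events. Section 6.3.7 says of Phase 1 only that people who withdraw voluntarily are removed.

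**The concern.** Two of the three quantities that Phase 1B sets out to estimate depend on people's opinion of the app, and the plan counts on hearing that opinion from a minority defined largely by having lasted the month. Persistence with an app is plausibly related to how usable and satisfactory it is. If so, the day-30 figures are selected on something close to the outcome, and a larger sample would not remove the selection.

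Phase 1 exists to develop and refine the app. People who stop in the first days could say what made them stop, and the plan describes no way of asking them. The protocol already has the remedy in Phase 3 but does not extend it to the phase that expects far heavier loss. The missing-data statement in 6.4.5 concerns the random effects logistic model for adherence and does not bear on Phase 1B satisfaction.

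**Working it through.** **Inputs.** Enrolment 250 (6.3.1). About 60% stopping after 3 days, about 30% lasting 30 days, target 60 (6.4.2). The 250 agrees with the stated total: 24 + 250 + 120 = 394 (5.3.1, 6.3.1).

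**Reproducing the target of 60.**
- Expected day-30 users: 250 × 0.30 = 75, not 60.
- Enrolment that would give 60 at 30% retention: 60 / 0.30 = 200, not 250.
- Using those still active after day 3: 250 × 0.40 = 100.
- 60 / 75 = 0.80, so 60 fits if 80% of day-30 users respond. No response rate is stated.

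The target can be reconciled with the plan's figures, but its basis is not given.

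**Who is missing.**
- Expected to supply data: 60 / 250 = 24%. If all 75 day-30 users replied: 75 / 250 = 30%.
- Without data: 76% (190 people) or 70% (175 people).
- Stopping after 3 days: 250 × 0.60 = 150. Stopping before day 30: 250 − 75 = 175. So 150 / 175 = 86% of the expected leavers go in the first days.

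**What this does to the estimate.** Let f be the fraction observed, p the proportion satisfied among respondents and q the proportion among everyone else. The all-enrolled figure is f·p + (1 − f)·q. The respondents' figure exceeds it by (1 − f)(p − q).

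The documents give neither p nor q. As an illustration only, assume p = 80%:

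| Assumed q | All enrolled, f = 0.24 | All enrolled, f = 0.30 |
|---|---|---|
| 20% | 34% | 38% |
| 40% | 50% | 52% |
| 60% | 65% | 66% |
| 80% | 80% | 80% |

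For example, 0.24 × 0.80 + 0.76 × 0.40 = 0.192 + 0.304 = 0.496. The last row shows no bias when the unobserved are as satisfied as the observed.

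**Limits with no assumption about q** (still p = 80%):
- 60 respondents: from 0.24 × 0.80 = 19% to 0.192 + 0.76 = 95%.
- 75 respondents: from 0.30 × 0.80 = 24% to 0.24 + 0.70 = 94%.

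The width is 1 − f, that is 76 or 70 points, for any p. The sampling half-width with 60 respondents is 1.96 × √(0.80 × 0.20 / 60) = 10 points, or 13 points at p = 50%. Non-observation, not sample size, is the main source of uncertainty.

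**The case against.** The strongest reply is that this is a development phase, described in the synopsis as iterative and qualitative. Phase 1B has no hypothesis or precision target, and no planned analysis in 6.4.3 uses its satisfaction figure. Attrition is itself a stated quantity and can be estimated on all 250, so a reader would see how selected the day-30 group is. Satisfaction among persisters is useful in its own right, and nothing says it will be presented as the view of all enrollees. Phase 1A also provides early feedback: 24 people use the app for one week and are then interviewed, on topics that include the interface and overall satisfaction. All of this stands. It limits the consequence but does not supply the views of Phase 1B leavers.

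Some stronger readings are tempting and are not supported:
- **That only current diary users will be asked.** No sentence says so. Sections 6.3.1 and 6.3.2 offer the optional month-end focus group without requiring continued use, and 60 is a hoped-for yield, not an eligibility rule. What can be said is that the target is derived from persistence and that no procedure for leavers is described.
- **That respondents stayed because they liked the app.** The documents give no reasons for stopping, and people may stop for reasons unrelated to the app.
- **That 60 is an arithmetic error.** It equals an 80% response among 75 completers. It is unexplained, not shown to be wrong.
- **That the raffle requires lasting the month.** Section 6.3.1 ties entry to completed participation without defining it, and section 7.1 states entry with no such condition.

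**Conclusion.** The point holds as a limited one. If the plan is followed as written, Phase 1B satisfaction and usability will come from about 24% of those enrolled, mainly persisters, with no described counterpart from those who stop. The figures probably overstate satisfaction and usability among all users. The direction rests on the judgement that people who find the app awkward or burdensome tend to stop sooner. The size is unknown: the table illustrates assumed values, and a reader should not take any row as an estimate of the bias. What follows without assuming anything about leavers is that 70 to 76 points of the all-enrolled figure are undetermined.

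The estimate of attrition is sound in principle. The Phase 2 analysis and the Phase 3 randomised comparison are not directly affected. This is a worthwhile, cheap improvement and not a flaw in the trial's main inference.

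**What to change.** In 6.3.1 (Phase 1B) and 6.4.2:
- Send a short REDCap survey on satisfaction, usability and reason for stopping to all 250 at day 30 regardless of diary use, and at formal withdrawal if that comes earlier.
- Do not trigger it by the two-missed-days contact used in Phases 2 and 3, and leave the raffle condition as it is. Two missed days is not discontinuation, and either change could alter the attrition that Phase 1B is meant to measure.
- Report results with all enrolled as the denominator and separately for stayers and leavers, with the response rate in each.
- State the basis for 60, for example 250 × 0.30 = 75 completers × an assumed 80% response = 60.

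The cost is one automated survey and a few lines of text; Phase 1B already uses REDCap for consent and email for contact. The drawbacks are incomplete response among leavers and later recall: those who stop after day 3 and do not formally withdraw would be asked about 27 days later. Partial response still helps. Each additional 25 respondents narrow the undetermined range by 25 / 250 = 10 points.
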